Note: this is being done for study quality, for correlation with confocal microscopy findings, and to identify patients with fungal and viral infection. Because culturing and PCR will take 2 to 8 days, during which time subjects thought clinically to have *Acanthamoeba* keratitis would be starting treatment before randomization, this assessment is not part of the inclusion criteria. Subjects who have been proven to have fungal and viral infections, if randomized on the basis of clinical and confocal microscope findings, will be removed from the study, even though they may have concomitant *Acanthamoeba* keratitis.

Subjects with a negative confocal microscopy evaluation but a positive PCR/Culture (confocal false negative) will **not** be enrolled in the study but treated with the best clinically available treatment outside the study.

Subjects meeting the inclusion criteria, including findings on slit lamp examination and confocal microscopy consistent with *Acanthamoeba* keratitis are entered into the study and randomized to one of the two treatment arms. They will then enter the Treatment Plan and Follow-up protocol as presented on page 16.

INCLUSION CRITERIA

Protocol section 4.1 Inclusion Criteria, page 33

Subjects must meet all of the following criteria to be considered eligible to participate in the study:

- 1. Subject must be able and willing to give informed consent.
- 2. Subject must be a man or woman of any race and ≥12 years of age, inclusive. Subjects <18 years will only be enrolled in selected study sites
- 3. Subject must be able to understand and willing to comply with study procedures, restrictions and requirements, as judged by the investigator.
- 4. Clinical findings consistent with Acanthamoeba keratitis

Clinical findings include the following:

- Epithelial lesions: epithelial punctate keratopathy, epithelial infiltrates, epithelial defects, dendritiform epithelial ulcers.
- Extracorneal lesions: limbal inflammation (limbitis), anterior scleral inflammation, diffuse or nodular.
- Stromal lesions: perineural infiltrates, anterior stromal infiltrates, disciform corneal swelling, stromal ulceration, ring abscess.
- Anterior chamber lesions: keratic precipitates, hypopyon.
- Late findings: fixed dilated pupil, mature cataract
- 5. Confocal microscopy findings consistent with *Acanthamoeba* keratitis (performed within 7 days prior to study entry or as part of screening procedures)

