All subjects at screening meeting the inclusion criteria and including those with negative confocal microscopy findings will have corneal scrapes for culture and histology of *Acanthamoeba*, and to perform *Acanthamoeba* deoxyribonucleic acid (DNA) identification by polymerase chain reaction (PCR).

Note: this is being done for study quality, for correlation with confocal microscopy findings, and to identify patients with fungal and viral infection. Because culturing and PCR will take 2 to 8 days, during which time subjects thought clinically to have *Acanthamoeba* keratitis would be starting treatment before randomization, this assessment is not part of the inclusion criteria. Subjects who have been proven to have fungal and viral infections, if randomized on the basis of clinical and confocal microscope findings, will be removed from the study, even though they may have concomitant *Acanthamoeba* keratitis.

Subjects with a negative confocal microscopy evaluation, but a positive PCR/Culture (confocal false negative) will not be enrolled in the study but will be treated with the best clinically available treatment outside the study.

Subjects meeting the inclusion criteria, including findings on slit lamp examination and confocal microscopy consistent with Acanthamoeba keratitis are entered into the study and randomized to one of the two treatment arms. They will then enter the Treatment Plan and Follow-up protocol as presented in figure 2: Schematic Presentation of the Treatment and Follow-up Protocol as presented in 5.3.

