4.2. Exclusion Criteria

Subjects who meet any of the following criteria will be excluded from participation in the study:

- 1. Subject with documented history and/or clinical signs of concomitant presence of an ocular infection caused by viruses (herpes simplex virus [HSV]) or fungi.
- 2. Subject treated with drugs having effects on *Acanthamoeba* cysts prior to study entry, including biguanides (PHMB, chlorhexidine) and diamidines (propamidine, hexamidine).
- 3. Subjects requiring systemic immunosuppression for *Acanthamoeba* associated scleritis.
- 4. Subjects requiring urgent surgical intervention for advanced *Acanthamoeba* keratitis in either eye (e.g., for advanced corneal thinning/melting etc.).

- 5. Subject with known or suspected allergy to biguanides, diamidines or intolerance to any other ingredient of the investigational treatments.
- 6. Subject affected by immunodeficiency diseases or taking systemic immunosuppressive therapy.
- 7. Subject with a major systemic disease or other illness that would, in the opinion of the investigator, compromise subject's safety or interfere with the collection or interpretation of study results.
- 8. If female, pregnancy, planned pregnancy, or breast-feeding.
- 9. Subject is participating in another interventional clinical study with an experimental or unapproved/unlicensed therapy or has participated in another interventional clinical study within 4 weeks prior to this study.

The investigator must ensure that all study enrolment criteria have been met at randomization. If a subject's status changes after randomization, but before the first dose of study drug is given such that he or she no longer meets all eligibility criteria, then the subject should be excluded from participation in the study.

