4.4. Subject Completion/Withdrawal

Any subject may voluntarily discontinue the study at any time without prejudice. The investigator may elect to discontinue a subject for reasons unrelated to the study drug (e.g. failure to comply with the study protocol, missed visits etc.), for reasons related to the study drug ([serious] adverse event ([S]AE])) or in case of treatment failure. In either event, reason(s) for discontinuation should be recorded on the CRF. Possible reasons for study discontinuation include the following:

Ocular intolerance.

- (S)AEs necessitating discontinuation from the study.
- Treatment failure.
- The subject is lost to follow-up.
- Subject decision not related to an (S)AE.
- Investigator decision (specify).
- Other reason (specify).

Subjects who miss up to 1 full day of treatment within the first 5 days after starting treatment or up to 2 full days of treatment after the first 5 days of treatment should not be discontinued, but will be classified as non-compliant. Subjects will be discontinued from the study if in the opinion of the investigator drug compliance is insufficient.

If the subject discontinues, all the end-of-study visit assessments must be performed, if possible. Moreover, the investigator should ensure (as far as possible) that all used and unused study drug has been collected from the subject. The subject will exit the study and be treated at the investigator's discretion. Discontinued subjects will not be replaced.

Subjects discontinued for (S)AE(s) will be followed-up after subject's discontinuation until the event is resolved or considered medically stable by the investigator. If necessary, the investigator may schedule further visits at his/her discretion. Data collected in the period up to the end-of-study visit will be recorded in the CRF. Data collected after Day 90 following the end of treatment, and related to the (S)AE that led to discontinuation will be recorded in the subject's medical record, and in the sponsor's Safety Database.

In case a subject is lost-to-follow-up, the investigator will attempt to contact the subject (by phone, letter or e-mail) at least twice.

A subject will be considered to have completed the study if all required assessments up to and including the 90 days after end of treatment and end-of-study assessments have been completed.

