7.1. Study Analysis Sets

7.1.1. Analysis Data Sets for the Efficacy Analyses

Full Analysis Set (FAS)

All subjects who have been randomized and for whom the primary efficacy variable is assessed will be included in the FAS. The FAS will be used in all efficacy analyses.

Per-Protocol Analysis Set (PPAS)

All subjects in the FAS without any relevant protocol deviations. The criteria for inclusion in the PPAS will be described in the SAP and documented before code breaking. The PPAS will be used in the analysis of the primary efficacy variable only.

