7.2 Analysis Sets

The decision on the classification of subjects to each analysis set will be taken at the clean file meeting, prior to breaking the blind, and documented in the clean file report together with the reasons for excluding subjects from analysis sets. Subjects who have not attended any visits where disease status is assessed, i.e. those who did not reach the day 30 visit, the first visit where disease status is recorded, will be classified as dropouts from the efficacy analysis sets. Any 30dayFU visit that is under the window, i.e. visit occurred too soon, will not be removed from the analysis population as long as the 90DayFU visit also proved that the patient was cured.

LINK Medical Study ID: PSR012

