7.2.1 Full Analysis Set (FAS)

All subjects who have been randomized and has a confirmed diagnosis of Acanthamoeba keratitis and for whom the primary efficacy variable has been assessed will be included in the FAS. The FAS will be used in all efficacy analyses. The last disease status assessment will be used for disease status assessment.

Analysis using the FAS will be based on the planned treatment (i.e. subjects will be analysed 'as randomised').

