7.9.1 Primary Efficacy Variable

The main endpoint disease resolution 12 months after baseline will be assessed at each visit up to study day 365.

Clinical resolution 12 months after baseline for a patient is defined as:

The percentage of subjects cured 30 days after discontinuing all study therapies, within 12 months of randomization. A clinical resolution classification requires a Yes response to the eCRF variable CRYN question: "Was clinical resolution obtained?" at one of the study visits from day 1 up to study day 365 in combination with a response *No* to the eCRF variable RELAPYN question "Did the subject experience relapse since the last visit?" at the pursuing visits, up to the last recording of this information. There should be no relapses after (the last) clinical resolution classification. Discontinued subjects will be regarded as not cured.

For patients defined as fulfilling disease resolution within 12 months, the date of the visit at which annotated CRYN is first answered with a Yes will be used as the date of resolution. The time-to-cure secondary variable will be the number of days from randomisation to the visit where resolution was recorded.

Since it is also possible to test for non-inferiority if the superiority hypothesis is not met, additional conditions are specified (see list below) to meet the strict requirements of a non-inferiority study, making it feasible to test for non-inferiority using the results from the superiority analysis, without a further separate analysis. The 90% CI for the difference between the treatments obtained from the superiority analysis gives the necessary information. Position of the lower end of the CI relative to a pre-defined agreed 0.20 non-inferiority margin (Δ) provides the key information for making decisions (conclusions) about non-inferiority.

PHMB has received the orphan drug designation. The use of 90% CI for the difference between the two treatments is to provide a 95% lower CI limit for non-inferiority.

The additional conditions specified to make testing for non-inferiority feasible are the following:

- Pre-defined non-inferiority margin (Δ =0.20) based on both clinical and statistical considerations, i.e., chosen on the basis of external information and not chosen to fit the data.
- Analysis of the FAS and the PPAS, giving similar results with respect to p-values and CIs for the
 efficacy measure at issue.

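### The SAP drops subjects with no Day 30 status from the efficacy sets but counts discontinued subjects as not cured, does not say which rule governs, and plans no CRR_12 analysis that shows the effect

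*SAP*

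**What the plan says.** **Who is analysed.** SAP 7.2 removes from the efficacy sets subjects who attended no visit at which disease status is assessed, explaining that "those who did not reach the day 30 visit, the first visit where disease status is recorded, will be classified as dropouts". SAP 7.2.1 requires randomisation, a confirmed diagnosis and an assessed outcome: only those "for whom the primary efficacy variable has been assessed will be included in the FAS". Protocol 7.1.1 has the assessment condition but no Day 30 rule: "All subjects who have been randomized and for whom the primary efficacy variable is assessed will be included in the FAS". SAP 7.9 bases all efficacy evaluation on the FAS. SAP 7.2.2 makes the PPAS a subset of it.

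**What outcome they get.** SAP 7.9.1 says "Discontinued subjects will be regarded as not cured", without a time limit.

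**Removals on pre-treatment grounds.** Protocol 3.1.2 provides that subjects with proven fungal or viral infection, "if randomized on the basis of clinical and confocal microscope findings, will be removed from the study". The timing is stated: "Because culturing and PCR will take 2 to 8 days". Protocol 4.2 also excludes a subject whose status changes after randomisation but "before the first dose of study drug is given such that he or she no longer meets all eligibility criteria".

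**What is reported.** SAP 7.3 gives set counts, withdrawals and primary withdrawal reasons by arm, and attendance at each visit.

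**The concern.** For someone who starts treatment and leaves before Day 30, the two rules give different answers. If 7.2 governs, a subject who leaves on Day 25 without an assessed status is absent from both efficacy sets, while one who leaves on Day 35, after the Day 30 assessment, is a failure. If 7.9.1 governs, both are failures.

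Early leaving can depend on treatment. Protocol 4.4 lists ocular intolerance and adverse events among the reasons for discontinuation, and the intensive 19-day course in Protocol 5.2 falls wholly before Day 30. Removing uncured leavers raises the observed cure rate of whichever arm loses more of them.

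No planned CRR_12 analysis would show this. The condition that FAS and PPAS results agree cannot detect losses common to both sets. SAP 7.1.5 refers sensitivity analyses to later sections, and the only one given for the primary variable is the PPAS. Blind classification at the clean file meeting prevents choosing by arm, but it does not undo selection on something that happened after randomisation.

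**Working it through.** **1. The plan's own figures.** Inputs from Protocol 7.6 and SAP 5.1: control 67% or 63%, difference 0.20, two-sided alpha 0.10, power 80%, 10% loss, 1:1 allocation. With unpooled variance, n per arm = [p1(1−p1) + p0(1−p0)] × (1.645 + 0.842)² / 0.20².
- 87% v 67%: 51.7, so 52 per arm. 104/0.9 = 115.6, giving the stated 116.
- 83% v 63%: 57.8, so 58 per arm, the stated 116 evaluable. 116/0.9 = 128.9, against the stated 130.

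The sample size is not in dispute. It fixes the setting: 65 randomised per arm, margin 0.20.

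**2. Excluding early leavers.** The documents give no early-leaving rates, so those below are assumed. Truth is defined on all randomised subjects, with leavers uncured. For leaving proportion L, the analysed rate is p/(1−L) on n = 65(1−L), rounded. The lower 90% limit is d − t(0.95; n1+n0−2) × s × √(1/n1 + 1/n0), where s² is the pooled residual variance of a linear model. Probabilities come from exact binomial enumeration. False non-inferiority is P(limit > −0.20) at 43% v 63%; false superiority is P(limit > 0) at 63% in both arms.

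Example, 5% v 0%: 0.43/0.95 = 0.453 on 62 subjects, against 0.63 on 65. A true −0.20 appears as −0.177. With equal true rates, 0.63/0.95 = 0.663 against 0.63, an apparent +0.033.

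| Early leaving, test v control | False non-inferiority | False superiority |
|---|---|---|
| 0% v 0% | 4.5% | 4.8% |
| 3% v 0% | 6.3% | 8.1% |
| 5% v 0% | 7.6% | 10.3% |
| 0% v 3% | 2.9% | 2.8% |
| 0% v 5% | 1.7% | 2.4% |
| 3% v 3% | 4.2% | 5.2% |
| 5% v 5% | 4.0% | 5.2% |

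Because the data are discrete, false non-inferiority with no leaving already moves between 4.1% and 5.2% as n per arm goes from 58 to 65. Differences of that order mean nothing.

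**3. Counting leavers as failures, with a different truth.** Suppose 43% v 63%, or equal 63%, hold among subjects followed. The analysed rate is then p(1−L) on 65. At 0% v 5%, control becomes 0.63 × 0.95 = 0.599, so −0.20 appears as −0.169.

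| Early leaving, test v control | False non-inferiority | False superiority |
|---|---|---|
| 0% v 3% | 7.1% | 7.4% |
| 0% v 5% | 9.3% | 9.6% |

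**4. One dataset under both rules.** Assume a cure rate of 63% in each arm among those reaching Day 30, with 10 early leavers on test and 3 on control. This puts all 13 planned losses before Day 30, so it is an extreme case. Wald 90% limits:
- Excluded: difference 0; lower limit −1.645 × √(0.2331/55 + 0.2331/62) = −0.147, inside the margin.
- Not cured: 0.63 × 55/65 = 0.533 against 0.63 × 62/65 = 0.601; difference −0.068, lower limit −0.210, outside the margin.

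**The case against.** **The sections read in sequence.** SAP 7.2 and 7.2.1 decide membership, 7.9 applies the FAS, and 7.9.1 assigns outcomes to those in it. This is the natural reading, and it stands. A reader might infer that the primary denominator is undefined; that is too strong. The sequence is still an inference, because under 7.9.1 a discontinued subject already has an outcome. If it is right, it confirms that the FAS depends on a post-randomisation event.

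**Not every early leaver is necessarily dropped.** Protocol 4.4 requires end-of-study assessments at discontinuation where possible, and the schedule of assessments includes a slit lamp examination at that visit. Resolution is a slit-lamp definition, so someone leaving on Day 25 may count as assessed. The documents do not say. The affected group may therefore be smaller than all early leavers.

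**Existing reporting is better than it first looks.** Attendance at each visit is planned (SAP 7.3), by default by treatment group (SAP 7.1.1), and reasons for exclusion from sets go into the clean file report. What is missing is a re-estimate of CRR_12 and withdrawal reasons split at Day 30.

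**The alternative is not safer under every truth.** Step 3 shows risks similar to those of exclusion. This stands, and it is why both analyses are needed. SAP 7.9.1 nevertheless supports failure as the intended outcome.

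**A tempting inference about direction.** Phase 1 reported dose-limiting events in 11.1% of healthy subjects on 0.08% PHMB (Protocol 1.1.2). A reader might conclude that the test arm will lose more subjects, so that exclusion favours it. That study had no propamidine arm, so it makes early leaving plausible but says nothing about the difference between these two regimens.

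**Conclusion.** The point holds as a gap in the plan that should be fixed. Precedence between the two rules is unstated, the likelier reading makes the primary set depend on a post-randomisation event, and no planned CRR_12 analysis shows the consequence.

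It would be wrong to conclude that the primary result is biased, or biased towards 0.08% PHMB. Early-leaving rates by arm appear nowhere, equal leaving has no material effect, and more leaving in control reverses the direction. If early leaving were 5% v 0% and leavers were uncured, exclusion would raise false non-inferiority from 4.5% to 7.6% and false superiority from 4.8% to 10.3%. These figures rest on the assumed rates, 65 randomised per arm and the 90% interval. SAP 7.9.1 also mentions a 95% interval for the non-inferiority decision, which is not used here.

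The rule for early 30-day follow-up visits and the 30-day and 90-day confirmation passages are separate wording matters. They form no part of this point.

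**What to change.** - In SAP 7.2 and 7.2.1, and in Protocol 7.1.1, state that the 7.9.1 rule prevails: randomised subjects with a confirmed diagnosis who discontinue after starting treatment and before Day 30 stay in the FAS, as randomised, as not cured.
- Allow exclusions only on pre-treatment grounds already in the documents, applied blind and identically in both arms: no confirmed diagnosis, fungal or viral infection proven on the screening scrape, or eligibility lost before the first dose. The carve-out matters. If 3 of 65 per arm (assumed) were co-infected and counted as failures, a true −0.20 would shrink to −0.20 × 62/65 = −0.19 and superiority power would be 78%, against 81% if they are excluded.
- Report CRR_12 and its 90% CI in the current assessed-only set as a sensitivity analysis.
- Add reasons for leaving before Day 30 by arm to the SAP 7.3 tables.
- If the sponsor keeps the assessed-only FAS as primary, the minimum is a CRR_12 sensitivity analysis counting early leavers as not cured.

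**Cost.** No new data are needed, since a not-cured outcome requires no Day 30 record. Both documents change, and SAP section 2 asks for a protocol amendment when principal features change. If 63% and 83% already count leavers as failures, 65 per arm gives about 83% power. If they apply only to subjects followed, counting leavers as failures rather than dropping them lowers power from about 82% to 80% at 3% early leaving per arm, and from 81% to 77% at 5%.

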7.1.4 Analysis Visit

An analysis visit is defined as a categorical variable used to classify values within an analysis variable into temporal or conceptual groups used for analyses.

The visits as defined in the case report form, CRF, will be used as analysis visits. The Schedule of Assessments table provide acceptable deviations from the specified study day at which study visits should occur. These are \pm 2 days up to study day 22, called study day 21 in the Schedules table, ref. section 7.1.3 above, \pm 3 days from study day 31 to 30 days after end of treatment (EoT), and \pm 5 days at the 90 day after end of treatment visit. A review of assessment times will be conducted before the clean file meeting. Necessary revisions will be documented in the Clean file report. Results tables will present statistics by visit number. Where deemed necessary, longitudinal analyses will use the observed durations from baseline. The mean duration in days between visits will be presented.

Study day windows

Study visit day	Target study day of visit	Window of study day visit
0	0	± 0 days
7	7	± 2 days
14	14	± 2 days
21	21	± 2 days
30	30	± 3 days
60	60	± 3 days
30 days after previous visit§ until resolution	30 after previous visit	± 5 days
30 days after EoT	30 days after EoT	± 3 days
90 days after EoT	90 days after EoT	± 5 days

[§] The protocol states "and every 30 ± 5 days until resolution". This is interpreted as 30 days after the previous visit, and not a multiplicity of 30 days based on a fixed setup from baseline, i.e. not 31+60+n*30.

In general, data from unscheduled visits will be presented in data listings only and not included in analysis or summary tables. An exception to this is data used to confirm eligibility in association with screening or randomisation where the last assessment will be considered in summaries of screening data.

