7.2.2 Per-Protocol Analysis Set (PPAS)

The per-protocol analysis set is defined as the subset of subjects in the FAS for whom no major protocol deviation judged as having an impact on the primary efficacy analysis was reported or identified. The last disease status assessment within 12 months of randomisation will be used for disease status assessment. For subjects with disease resolution at that last visit, the 30-day and 90-day follow-up assessments should confirm disease resolution. Otherwise, the disease will be regarded as not having been resolved.

The decision as to which protocol deviations should be considered as reason for exclusion from the PPAS should be made at the clean file meeting and documented in the clean file report.

Analysis on the PPAS will be based on the actual treatment (i.e. subjects will be analysed 'as treated'). The primary efficacy variable, CRR_12, will also be evaluated using the PPAS.

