7.4 Protocol Deviations

Protocol deviations will be presented in a data listing.

The number and percentage of randomized subjects with at least one major protocol deviation leading to exclusion from an analysis set will be presented.

Major deviations are those deviations that could affect the scientific integrity of the study:

- Did not comply with the allocated treatment
- Did not attend the two follow-up visits

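### SAP 7.2 makes retention of subjects with a too-early 30-day follow-up visit depend on cure at 90 days, in conflict with 7.2.1, 7.2.2, 7.4 and 7.9.1

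*SAP*

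**What the plan says.** The general part of SAP 7.2 leaves the classification of subjects into analysis sets to the clean file meeting, before the blind is broken. It adds that a 30-day follow-up visit below its window "will not be removed from the analysis population as long as the 90DayFU visit also proved that the patient was cured". The window table in SAP 7.1.4 allows 3 days either side of day 30 after end of treatment, so too soon means before day 27. The sentence refers to an analysis population without naming the FAS or the PPAS. It does not say what happens if the 90-day visit shows disease or was not made.

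Four other sections bear on the same subject:

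- SAP 7.2.1 defines the FAS as "All subjects who have been randomized and has a confirmed diagnosis of Acanthamoeba keratitis and for whom the primary efficacy variable has been assessed". It contains no visit-window or 90-day condition.
- SAP 7.2.2 (PPAS) requires the 30-day and 90-day assessments to confirm resolution, and then says: "Otherwise, the disease will be regarded as not having been resolved".
- SAP 7.9.1 says: "There should be no relapses after (the last) clinical resolution classification". It also says: "Discontinued subjects will be regarded as not cured".
- SAP 7.4 lists two major deviations: not complying with the allocated treatment, and "Did not attend the two follow-up visits". An early visit is not listed.

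**The concern.** A condition on not being removed has an effect only if failing the condition can lead to removal. Two subjects with the same timing deviation could then be treated differently because of outcome: the one cured at 90 days stays, and the one not cured can leave. That is selection on the result that the analysis set is meant to measure. Taking the decision before unblinding does not prevent it, because cure status is visible at the clean file meeting even when treatment is not.

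The denominator of CRR_12 is at stake, and with it the lower confidence limit that decides non-inferiority. SAP 7.9.1 also requires the FAS and PPAS to give similar results before non-inferiority is claimed. If the sentence were applied to both sets, both would shift together and that check might not show it.

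**Working it through.** **1. Number per arm.** Inputs from SAP 5.1: control 63%, true difference 0.20 (so 83%), two-sided alpha 0.10, power 80%, 10% loss, 116 evaluable of 130. With the unpooled two-proportion formula:

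n per arm = (1.645 + 0.842)² × [0.63×0.37 + 0.83×0.17] / 0.20² = 6.185 × 0.3742 / 0.04 = 57.9, so 58.

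Two arms give 116, the plan's evaluable number. Dividing by 0.90 gives 129, against 130 stated. I therefore use 58 per arm.

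**2. The sections side by side, for a subject with resolution recorded within 12 months and an early 30-day visit.**

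| 90-day status | SAP 7.2 sentence | Other SAP sections |
|---|---|---|
| Cured | Kept | Kept; cured if there is no relapse after the last resolution |
| Relapse after the last resolution | Silent; by its converse, removable | 7.2.1: in the FAS. 7.9.1: not cured. 7.2.2: not resolved |
| No 90-day visit | Silent; by its converse, removable | 7.2.1: no 90-day condition. 7.9.1: judged on relapse answers up to the last recording; not cured if discontinued. 7.2.2: not resolved. 7.4: possible major deviation for non-attendance |

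In the second row the instructions are incompatible. In the third, 7.2 adds a route to removal based on visit timing that no other section contains.

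**3. Effect on one arm.** With x cures among n = 58, removing k failures changes the rate from x/58 to x/(58 − k). The documents give no count of early visits, so k is an assumption.

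| Cures | All kept | k = 1 | k = 3 | k = 5 |
|---|---|---|---|---|
| 37 (near 63%) | 63.8% | 64.9% (+1.1) | 67.3% (+3.5) | 69.8% (+6.0) |
| 48 (near 83%) | 82.8% | 84.2% (+1.5) | 87.3% (+4.5) | 90.6% (+7.8) |

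The shift can also go the other way. If the removed subject had no 90-day visit but would count as cured under 7.9.1, the rate moves from 37/58 = 63.8% to 36/57 = 63.2%, a fall of 0.6 points.

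**4. Effect on the difference (test minus control).** The interval is a Wald 90% interval, standing in for the model-based one:

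p₁ − p₂ ± 1.645 × √[p₁(1 − p₁)/n₁ + p₂(1 − p₂)/n₂]

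- Equal removal of failures, 48 versus 37 cures: 11/58 = 0.190 with none removed, 11/57 = 0.193 with one per arm, 11/53 = 0.208 with five per arm.
- Removal in the test arm only, 34/58 versus 37/58: the lower limit is −0.2003, which misses the 0.20 margin. With one test-arm failure removed (34/57) it is −0.190, which meets it.
- Removal in the test arm only, 33/58 versus 37/58: the lower limit moves from −0.218 to −0.199 with two removed.

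The last two cases are chosen to lie near the margin. They show what could happen, not what is likely.

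**The case against.** A reader might infer that relapsed subjects are dropped from the primary analysis instead of being counted as failures. The documents do not support that as a statement of fact. No section says such a subject is removed; it is only the converse of the condition. The grammatical subject of the sentence is a visit, not a patient. A visit before day 27 cannot show 30 relapse-free days and a clean 90-day visit can, so the sentence may mean only that the early visit is acceptable when the later one confirms cure. Failing that, 7.2.2 makes the subject a failure who stays in the denominator.

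The reach to the FAS rests on placement alone. The sentence stands in the general part of 7.2, after one about the efficacy analysis sets, but only the PPAS definition requires 30-day and 90-day confirmation, and SAP 7.9 makes the PPAS supportive.

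Nor is every relapse a failure. Under the Protocol (Schedule of Assessments, note 3, and 5.3.3), treatment restarts after a culture-negative relapse within 11 months (Day 335), and 7.9.1 looks to the last resolution. A relapsed and re-treated subject can still count as cured.

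All of this stands, and it limits the point to a conflict between sections. It does not remove the conflict: the benign reading has to be supplied by the reader, and the clean file meeting would choose between readings with outcomes in view.

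**Conclusion.** The point holds as a conflict. SAP 7.2 makes retention of early-visit subjects conditional on cure at 90 days, names no analysis set, and leaves the other outcomes unstated, while 7.2.1, 7.2.2, 7.4 and 7.9.1 point to keeping such subjects and classifying them by outcome. If failures were removed, each would raise that arm's CRR_12 by about 1.1 to 1.5 points, assuming 58 evaluable per arm and rates near 63% and 83%.

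A reader might go further and infer that CRR_12 is biased upward in both arms, or that the treatment difference is biased in a known direction. The documents do not support either. The number of early visits is not given, subjects without a 90-day visit may be apparent cures, and equal removal in the two arms moves the difference by only 0.003 for one failure per arm in the example. One subject could decide non-inferiority only if the result lay very close to the margin.

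**What to change.** Replace the early-visit sentence in SAP 7.2 with:

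> An early 30-day follow-up visit never removes a subject from the FAS. The subject's outcome is classified by section 7.9.1, using the last clinical resolution within 12 months. A subject with relapse after that last resolution is counted as not cured and stays in the denominator. A missing 90-day visit is handled by the same rule as for any other subject. If visit timing is used for the PPAS, it applies to all early visits whatever the 90-day result.

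The reference to the last resolution matters: a blanket rule that any later relapse means not cured would misclassify subjects who relapse, are re-treated and then resolve within 12 months.

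The cost is this one SAP passage, settled before the clean file meeting, with no new data. CRR_12 may come out slightly lower than if failures were removed.
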